### Anesthetic Technique

Before administering any medications a baseline inspired volume via an incentive spirometer in the holding area will be obtained. The type of anesthesia (general endotracheal) will be consistent with standard practice at Stony Brook and many other centers. Induction of general anesthesia will be achieved by an induction agent such as propofol [1 to 2.5 mg/kg (lean body mass)] combined with bolus doses of fentanyl. Should a rapid sequence induction be desired based on the patient's co-morbid conditions (reflux disease, etc.), succinylcholine or rocuronium may be used to obtain paralysis for intubation. In the event that succinylcholine is used, the patient will be allowed to obtain a full return of muscle strength (TOF 4/4), prior to administration of rocuronium for further paralysis during the surgery. Induction drugs and dosing may be modified at the discretion of the clinical anesthesia team. Maintenance of anesthesia will be achieved either through the use of volatile inhaled agents or intravenous anesthetic. The choice of agents for maintenance will be based upon the discretion of the anesthesiologist.

### Neuromuscular monitoring

Neuromuscular monitoring is standard of care for general endotracheal anesthesia. In this study neuromuscular function will be monitored using the TOF-watch SX acceleromyograph (MSD BV, Haarlem, The Netherlands) at the adductor pollicis muscle. The thumb is attached to a flexible adaptor that applies a constant preload to the thumb. Neuromuscular stimulation will be applied to the ulnar nerve via two pediatric electrodes applied on the skin left and right of the ulnar nerve at the distal forearm. Before administration of any neuromuscular blocking agent, but after induction of general anesthesia, the following procedures will be conducted to standardize the neuromuscular monitoring: (1) application of a tetanic ulnar nerve stimulation (50 Hz for 5 seconds); (2) calibration of the TOF-watch (CAL 2); (3) performance of a series of TOF measurements, to ensure that the TOF ratio differs by less than 5% between measurements (if the TOF ratio differs by more than 5%, the TOF-watch will be recalibrated). After these steps, the neuromuscular blocking agent according to protocol is administered. In patients requiring rapid sequence induction, succinylcholine will be used for intubation and after return of 4/4 twitches, the aforementioned steps (steps 1-3) will be conducted. When, during the study, the number of measured twitches is zero, the PTC will be measured. A 50 Hz tetanic stimulation for 5 s is followed (after a 3 s rest) by 15 single stimulations at 1 Hz. The number of twitches generated (that is, the PTC) corresponds with the degree of NMB, with a PTC of 1 to 2 reflecting a deep level of NMB.

## Ventilation

The mode of ventilation for these cases will be standardized consistent with routine practice. All of the patients will receive volume-controlled ventilation at a tidal volume of 6-8 ml/kg (5 cm PEEP). The respiratory rate will be adjusted at the discretion of the anesthesiologist to maintain an end-tidal CO2 of 30-40 mmHg during the surgical procedure.

## Study measurements during anesthesia

### **Primary Outcomes**

Peak Airway Pressures: Airway pressures will be measured every 1 minute.

### **Secondary Outcomes**

Mean Airway Pressure: In addition to the Peak airway pressure, the mean airway pressure will also be recorded every 5 minutes during the procedure.

## Hemodynamic monitoring

Blood pressure and heart rate will be measured using the noninvasive blood pressure cuff and standard three lead EKG, respectively every 1 minute during the interval in which the peak airway pressures are being measured (“deep” vs. “moderate”).

## Additional variables

Additional variables will include duration of surgery, drug dosages (propofol, opioids, muscle relaxant, reversal agent, glycopyrrolate, other agents used during anesthesia), and duration from reversal to extubation. Standard extubation criteria will be (SpO2 >98% on 100% FiO2, RR <35, TV > 5 ml/kg).

## Surgical rating

During the procedure, the surgical condition will be scored by the surgeon using a five-point SRS. To reduce variability in the surgical rating, all surgeries will be performed by a core group of surgeons who will receive training in how to report this information.

The rating scale will be a five-point ordinal scale ranging from 1 = poor condition to 5 = optimal surgical conditions (see appendix, Table 1). The surgeon scores the condition at 15-minute intervals. In case of a sudden change in surgical conditions, additional scores are obtained. If conditions are poor (score 1 or 2), muscle relaxation can be increased (in effect converting patient from moderate to deep according to methodology specified in this protocol using the rocuronium infusion).

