## **Background**

The frequency of surgical procedures that can be performed laparoscopically is rapidly increasing. Surgical conditions in laparoscopic surgery are largely determined by the depth of neuromuscular relaxation during surgery. Neuromuscular blockade (NMB) is frequently utilized in laparoscopic procedures to improve surgical conditions by relaxing the abdominal muscles and thus facilitating insufflation with CO2 to optimize surgical view. While studies have investigated the effects of neuromuscular blockade on surgical conditions and abdominal insufflation pressures, to our knowledge, little is known about the benefit, if any, a deep NMB blockade will have over a moderate NMB on airway pressures. Increased airway pressures can lead to an increase in alveolar and perivascular edema, a decline in dynamic lung compliance and hypoxemia. A deep neuromuscular blockade could decrease the resistance to ventilation by increasing the compliance of the chest and abdominal wall, thereby allowing maximization of lung expansion at lower airway pressures.

Several studies have investigated surgical view under deep vs. moderate neuromuscular blockade. Across a single intraabdominal insufflation pressure, a deep neuromuscular blockade may provide better surgical conditions than a moderate block. Raising the intraabdominal insufflation pressure can result in several adverse outcomes such as increased airway pressures, postoperative pain, risk of CO2 embolism, and hemodynamic disturbances. Low insufflation pressures of < 12 mm Hg have been associated with fewer adverse effects than higher pressures (>15 mm Hg). Though studies have shown that surgical view under deep block is statistically superior to the view under a moderate NMB block across a single insufflation pressure, the primary outcome in these studies was a subjective, 5 point scale requiring the surgeon to grade his surgical view. Hence, there is a lack of objective outcomes assessed in these studies. Measuring the peak airway pressures in the deep vs. moderate block group will provide us with an objective indice to use in making the determination if one type of block is ‘superior’ to the other.

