Upon successful acclimation to a “moderate” NMB, data collection may begin again (T2): the surgeon will again provide the SRS score simultaneously with the commencement of collection for peak airway pressure and related values. For the next 20 minutes of surgery during which a “moderate” NMB is maintained, peak airway pressure measurements (as well as other relevant secondary outcome measurements) will be collected every minute by the study team member by looking at the anesthesia machine’s readings and the surgeon will provide the SRS score every 5 minutes. After 20 minutes (T3), the patient will remain at the “moderate” NMB for the duration of the surgery unless a change in the depth of blockade is requested by the surgeon. Should such a request be made, this will be documented in the data collection (obtained from anesthesia record) along with the depth of blockade that the patient was switched to. By skin closure, the patient’s NMB will be returned to “moderate.”

Group 2 M→D: After induction and intubation, the patient will be maintained in a “moderate” (one or two twitches) neuromuscular block (NMB). Moderate NMB will be obtained with intubating dose of rocuronium of 0.5 mg/kg or as per clinical team’s discretion. After surgical incision is made, the abdomen is insufflated, trocars are inserted and prior to the beginning of the actual laparoscopic procedure, collection of data for “moderate” NMB period will begin. Neuromuscular blockade level will be maintained and adjusted throughout the course of surgery

using intravenous bolus doses of rocuronium. Dosing of rocuronium will be determined by the clinical team. Only the clinical team will administer any medications or fluids to patients enrolled in the study (no research team members will be administering drug or fluid). The surgeon will inform the study team member of the first SRS score for his/her view, and simultaneously, the initial peak airway pressure and related values are collected (T0). For the next 20 minutes of surgery (during which a “moderate” NMB is being maintained), peak airway pressure measurements, heart rate, and blood pressure will be collected every minute by the study team member by looking at the anesthesia machine’s readings, and the surgeon will provide the SRS score every 5 minutes.

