Intraoperative and postoperative data will be collected by a research coordinator who is not blinded to the patient’s randomization. The research coordinator will not be directly involved with the patient’s care. Rather, his/her sole purpose will be to record the relevant data (airway pressures, abdominal insufflation pressures, PACU indices etc.) every 1 minute. The coordinator will have

access to the electronically recorded patient data and will make their recordings directly from the anesthesia machine and/or the electronic anesthesia record. The research coordinator will also review data from the patient's chart (anesthesia record, PACU record) after surgery to collect any additional information that may be necessary.

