#### *Surgical rating scores*

Summary statistics (mean  $\pm$  standard deviation, median, IQR) will be computed for surgical rating scores for each patient, per each treatment group. Wilcoxon sign rank tests will be used to compare surgical rating score between the two groups. P-values will be reported and 95% confidence interval of group difference will also be reported.

*Numerical pain rating, occurrence of nausea or vomiting, and level of sedation or alertness*  
Numerical pain rating score and level of alertness will be presented as a graphical display of treatment group mean or median over each of the four time points in the recovery room. Contingency table (condition\*group\*time) for nausea/vomiting will be presented. GEE (Generalized estimating equation) will be used to compare the recovery room variables between the two treatment conditions with time and treatment group as covariates. Exchangeable correlation structure will be applied. The distribution of binary variable (occurrence of nausea or vomiting) is assumed to binomial, and the distribution of other ordinal variables are assumed to poisson or negative-binomial based on the nature of data.

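### No stated step keeps the surgeon unaware of block depth when giving the surgical rating, and the text conflicts on whether a low rating may deepen the block inside the moderate measurement window

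*Combined protocol and SAP*

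**What the plan says.** Under Surgical rating, "the surgical condition will be scored by the surgeon using a five-point SRS". Under Investigational plan and treatments, a score is given at the start of each 20-minute window and then "the surgeon will provide the SRS score every 5 minutes", under both depths in every patient. The SAP section Surgical rating scores states that "Wilcoxon sign rank tests will be used to compare surgical rating score between the two groups".

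The one control on rating quality is that "all surgeries will be performed by a core group of surgeons who will receive training in how to report this information"; its stated aim is to reduce variability. The one statement about masking is that "Intraoperative and postoperative data will be collected by a research coordinator who is not blinded to the patient" and the patient's allocation. Nothing in the readable text says whether the surgeon knows the sequence, sees the neuromuscular monitor or observes dosing.

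The Background criticises earlier work because "the primary outcome in these studies was a subjective, 5 point scale requiring the surgeon to grade his surgical view". Its table of risks and benefits then records that the literature favours deep block for operating view.

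On changes of depth, Surgical rating says: "If conditions are poor (score 1 or 2), muscle relaxation can be increased (in effect converting patient from moderate to deep". It sets no limit on when this may happen. Investigational plan and treatments describes each depth as maintained through its 20-minute window. It mentions a surgeon's request only for the time after T3, when the depth is kept "for the duration of the surgery unless a change in the depth of blockade is requested by the surgeon".

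The Statistical Analysis section summarises readings by patient and treatment period. It has no rule for readings or scores taken after a triggered deepening.

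**The concern.** There are two separate problems.

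**Rating.** The same surgeon rates both depths in the same patient within one operation. A surgeon who knows the depth and expects deep block to give a better view may score it higher without any real difference. That shift goes straight into the paired difference, and the signed rank test cannot tell it from a treatment effect. Training does not remove it: trained raters who know the depth can be consistent and still biased. No later analysis can separate the two.

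**Exposure.** Peak airway pressure is recorded every minute in the windows in which the surgeon scores. If a low score leads to deepening inside the moderate window, part of that window is no longer moderate. Analysed as moderate, those readings pull the two conditions together and dilute the primary contrast.

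**Working it through.** **1. The plan's own figure.** Inputs from Power analysis: difference 1.48 mmHg, SD 3.68 mmHg, alpha 0.05, 52 patients. The SD is taken as that of the paired difference and the test as two-sided. The noncentrality is 1.48/3.68 × √52 = 2.90, the critical value is t(0.975, 51) = 2.008, and the power is 81.2%. The stated figure of about 81% reproduces. It concerns peak airway pressure; the documents give no effect size or SD for the surgical rating.

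**2. Expectation shift in the rating.** Let b be the mean shift in favour of deep block and s the SD of the paired difference in scores. Both are assumed. With no true effect, the rejection rate is P(|T| > 2.008), where T is noncentral t with 51 degrees of freedom and noncentrality b/s × √52. This is a paired-t approximation to the planned signed rank test. For example, b = 0.25 and s = 1.0 give 0.25 × 7.211 = 1.80 and a rate of 42%.

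| Shift b (points) | s = 0.8 | s = 1.0 | s = 1.2 |
|---|---|---|---|
| 0.05 | 7% | 6% | 6% |
| 0.1 | 14% | 11% | 9% |
| 0.25 | 60% | 42% | 31% |
| 0.5 | 99% | 94% | 84% |

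The nominal rate is 5%. A larger sample makes this worse, because bias does not shrink with n. At the planned enrolment of about 120, a shift of 0.1 gives 15–27% and a shift of 0.25 gives 62–92%.

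**3. Conversion of moderate windows.** Let f be the share of patients whose whole moderate window is in fact deep but analysed as moderate (assumed), with the SD unchanged. The expected difference becomes 1.48 × (1 − f).

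| f | Difference (mmHg) | Power, n=52 | Power, n=120 |
|---|---|---|---|
| 0 | 1.48 | 81% | 99% |
| 10% | 1.332 | 73% | 98% |
| 20% | 1.184 | 62% | 94% |

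If conversion comes halfway through the window, the loss per patient is halved, and power at n=52 is 77% for f = 10% and 73% for f = 20%.

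**4. The sections side by side.** Surgical rating ties deepening to a score of 1 or 2 at any time. Investigational plan and treatments holds depth through each window and places surgeon requests after T3. The two also differ on the scoring interval (15 against 5 minutes) and on rocuronium by infusion against bolus. The text does not settle whether conversion inside a window is permitted.

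**The case against.** The strongest reply is that the plan has already dealt with subjectivity. It makes peak airway pressure, a machine reading, the primary outcome for exactly that reason, and it does not list the surgical rating among the outcomes under Objectives. This stands, and it limits the weight of the rating problem. A reader might infer that the plan repeats the fault it criticises, or that unmasked scoring biases the primary measurement. The documents support neither. The rating is an additional endpoint, though formally tested, and the only route to the primary outcome is a change in the depth actually delivered.

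That route is itself uncertain. A reader might infer that biased scores will alter the moderate window, but Investigational plan and treatments describes depth as maintained there. What can be shown is a conflict between sections and a missing analysis rule.

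A reader might also infer that the rating comparison must be biased towards deep block. Expectation could push that way, but deepening after low moderate scores would bring the two windows together. The net direction is undetermined.

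The rejection rates depend on the assumed shifts. At 0.05 points the rate is barely above nominal, and nothing in the documents says which shift is likely.

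Finally, Figure 1 and some front matter were not available for this review, so masking stated only there cannot be ruled out. The finding is that the readable text states none.

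**Conclusion.** The point holds in two limited parts.

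First, the surgeon's rating is compared between depths with no stated step to keep the surgeon unaware of depth, so a positive result could reflect expectation. At n=52 the false-positive rate would be 9–14%, 31–60% or 84–99% for assumed shifts of 0.1, 0.25 or 0.5 points. These figures rest on an assumed SD of 0.8 to 1.2 and a paired-t stand-in for the signed rank test; they illustrate sensitivity and do not estimate the bias.

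Second, the sections conflict on whether a low score may convert a moderate window to deep, and the analysis has no rule for that case. If 10% or 20% of windows were fully converted, power at n=52 would fall to 73% or 62%; with 120 analysed patients it would stay at 98% or 94%. The conversion shares are assumed.

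Masking addresses only the first part: a genuine low score from a masked surgeon could still trigger deepening. The change is worth making before enrolment, but the point does not undermine peak airway pressure as a measurement.

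**What to change.** - **Masking.** In Investigational plan and treatments and in Surgical rating, state that the surgeon is not told the sequence or current depth, that the TOF-watch display and dosing are kept out of the surgeon's view, that the coordinator asks for the score with a fixed prompt, and that any unblinding is recorded. Disclosure stays allowed whenever care requires it. If masking is not feasible, say so and report the rating as unmasked.
- **Consistency.** Reconcile Surgical rating with Investigational plan and treatments on when deepening after a low score may occur, on the scoring interval and on infusion against bolus. Which clinical rule applies is for the investigators to decide.
- **Analysis.** In Statistical Analysis and in Surgical rating scores, pre-specify how peak-pressure readings and ratings after a triggered deepening are analysed, and report the number of conversions by sequence.

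The cost is protocol and SAP wording and a small change to theatre set-up. The coordinator already takes the scores, so the text suggests no need for extra staff. The downside is that masking may be imperfect: a fresh score after the transition period can itself signal the switch.

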### Study measurements in the post-anesthesia care unit

In the recovery room, the following variables will be measured by a different study personnel, when possible, at 15 min intervals for the first 1 hour: respiratory rate, arterial oxygen saturation, numerical pain rating (on a scale from 0, no pain, to 10, most severe pain imaginable), occurrence of nausea or vomiting, and level of sedation or alertness. The level of sedation/alertness will be assessed in the recovery room using the validated Leiden Observer's Assessment of Alertness/Sedation (see appendix, table 2). Additionally, the patient's maximum inspired volume will be assessed 30 minutes after arrival in the PACU via the use of an incentive spirometer.

### Post-operative day 1 follow up

QoR 9 on post op day 1 (via phone or in person)

### Other parameters

Time to optimal extubation conditions from the moment of reversal (with optimal conditions defined as TOF 4 with ratio >90%), time in the post-anesthesia care unit, and drug consumption will be recorded.

### Safety evaluations

Serious adverse events (SAE) that occur during the study will be recorded in the case report form. The AE record in the case report form includes the nature of the event (with onset date and time, end date and time), severity, treatment, outcome, and the relationship to the treatment given. All AEs that meet reporting criteria will be reported to the medical ethics committee and authorities, as required by the GCP/GRP guidelines.

### **Statistical Analysis**

*Airway Pressure, Intra-abdominal pressure, Respiratory rate, arterial oxygen saturation, blood pressure, heart rate*

In order to obtain the most accurate measurements possible, multiple readings for the primary outcome (peak airway pressure) and secondary outcomes (respiratory rate, arterial oxygen saturation, blood pressure, and heart rate) will be collected once per minute for a maximum of 20 minutes per treatment period. Summary measures (i.e. descriptive statistics including mean  $\pm$  standard deviation, median, and interquartile range) for each data element will be generated for each patient, per each treatment period. Depending on the distribution of the peak airway pressure variable (as tested by Shapiro-Wilk tests), either a paired t-test or Wilcoxon Sign Rank test will be used to compare peak airway pressure between the two treatment conditions. Secondary outcomes

(respiratory rate, arterial oxygen saturation, blood pressure, and heartrate) will also be examined in a similar way for differences between the two treatment groups. P-values will be reported at the 95% confidence level.

Additionally, linear mixed effects models will be used for the peak airway pressure outcome, with treatment group and time as fixed effects, and subject as random effect. Group effect size and p-value will be reported at the 95% confidence level.

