## **Objectives**

Primary Outcome: Peak Airway Pressures

Secondary outcomes:

- Hemodynamics (blood pressure (BP), Heart rate (HR)) measured q15 min at the time of airway pressure measurement
- Duration from administration of sugammadex (to be given at skin closure) to Train of Four (TOF) ratio = 0.7, 0.8 and 0.9 and extubation using the following guidelines (SpO2 >98% on 100% FiO2, Respiratory rate (RR) <35, tidal volume (TV) > 5 ml/kg, RR/Tidal Volume <100)
- Recovery variables in the post-anesthesia care unit (respiratory rate, arterial oxygen saturation, numerical pain rating, nausea or vomiting, and level of sedation or alertness).
- Adverse events (AE).

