To minimize any type of carry-over effects, after completion of the moderate NMB 20 minute period, a “transition period” will begin (T1). During this “transition period” additional IV bolus doses of rocuronium will be administered to the patient to achieve “deep” neuromuscular blockade. Upon successful acclimation to a “deep” NMB, data collection may begin again (T2): the surgeon will again provide the SRS score simultaneously with the commencement of collection for peak airway pressure and related values. For the next 20 minutes of surgery (during which a “deep” NMB is maintained), peak airway pressure measurements (as well as other relevant secondary outcome measurements) will be collected every minute by the study team member by looking at the anesthesia machine’s readings, and the surgeon will provide the SRS score every 5 minutes. After 20 minutes (T3), the patient’s “deep” NMB will be maintained for the duration of the surgery unless a change in the depth of blockade is requested by the surgeon. Should such a request be made, this will be documented in the data collection (obtained from the anesthesia record) along with the depth of blockade that the patient was switched to. By skin closure, the patient’s depth will be returned to “deep.”

(Both Group 1 and Group 2): At skin closure, subjects in both groups will be reversed with sugammadex 4 mg/kg or at the discretion of the clinical team (T4). Patients will be extubated when the TOF ratio becomes 0.9 or higher (T5). Time from administration of sugammadex to extubation will be recorded.

In the recovery room (T6), the following variables will be measured by the study coordinator at 15 min intervals for the first 1 hour: respiratory rate, arterial oxygen saturation, numerical pain rating (on a scale from 0, no pain, to 10, most severe pain imaginable), occurrence of nausea or vomiting, and level of sedation or alertness. Additionally, the patient’s maximum inspired volume will be assessed 30 minutes after arrival in the PACU via the use of an incentive spirometer. After one hour, all measurements will be complete (T7).

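### Are recovery-room respiratory rate and oxygen saturation left without a usable analysis?

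*Combined protocol and SAP*

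**What the plan says.** The Objectives list, among the secondary outcomes, "Recovery variables in the post-anesthesia care unit (respiratory rate, arterial oxygen saturation, numerical pain rating" and so on to nausea or vomiting and sedation. The Investigational plan says that these "will be measured by the study coordinator at 15 min intervals for the first 1 hour: respiratory rate, arterial oxygen saturation", and the section on PACU measurements repeats the schedule. All of these readings come after both treatment periods and after reversal.

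The opening part of the Statistical Analysis also names rate and saturation as secondary outcomes. There the readings "will be collected once per minute for a maximum of 20 minutes per treatment period", are summarised per patient and period, and are tested as peak airway pressure is, by paired t-test or signed-rank test: "respiratory rate, arterial oxygen saturation, blood pressure, and heartrate) will also be examined in a similar way for differences between the two treatment groups".

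The recovery-room analysis stands under the heading "Numerical pain rating, occurrence of nausea or vomiting, and level of sedation or alertness". Its GEE "will be used to compare the recovery room variables between the two treatment conditions with time and treatment group as covariates", with exchangeable correlation. The family is binomial for nausea or vomiting, and "the distribution of other ordinal variables are assumed to poisson or negative-binomial based on the nature of data".

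**The concern.** Read quickly, the two variables fall between two analyses. Where the analysis plan names them, it prescribes a within-patient contrast of deep against moderate block, and no patient has such a pair in the PACU. The recovery-room heading leaves them out. The families given there are for binary and ordinal data, and rate and saturation are neither.

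The intraoperative rate raises a further doubt. The Ventilation section says "The respiratory rate will be adjusted at the discretion of the anesthesiologist", towards an end-tidal CO2 range, so a paired p-value for it would partly describe ventilator adjustment. If that p-value were reported as the declared respiratory outcome, a reader would be misled. At stake are two of five PACU outcomes, all secondary.

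**Working it through.** **1. The plan's own figure.** The only power statement is for the primary outcome: difference 1.48 mmHg, SD 3.68, 52 patients, α 0.05. The standard error is 3.68/√52 = 0.510 and 1.48/0.510 = 2.90. The two-sided noncentral t gives 81.2%, against the stated 81% or so. Nothing below touches it.

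**2. Which readings enter which analysis.**

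- *Intraoperative.* Readings are taken each minute in both periods, so every patient contributes a deep and a moderate summary and pairing is right. The Investigational plan names airway pressure, heart rate and blood pressure, but also provides for related values and other secondary measurements, with a coordinator recording every minute. Intraoperative rate and saturation fit that description.
- *PACU.* There are four readings over an hour, and each patient belongs to one sequence. The comparison is between groups: 52/2 = 26 per sequence at the calculated sample size, 120/2 = 60 at planned enrolment.
- *The GEE.* Its operative sentence is about the recovery-room variables, and the protocol's list of what is measured there includes rate and saturation. Treatment group as a covariate can only be the randomised group. The section on time from reversal to extubation likewise compares independent groups.

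A between-group longitudinal model is therefore assigned to PACU rate and saturation. What it lacks is a stated family.

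**3. How poor the named families would be.** The documents give no PACU means, SDs or correlations, so all of those below are assumptions. Poisson sets variance/mean to 1.

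- Saturation, mean 95–99, SD 1–3: 1/99 = 0.010 to 9/95 = 0.095. At mean 97 the Poisson SD is √97 = 9.85.
- Rate, mean 12–20 per minute, SD 2–4: 4/20 = 0.20 to 16/12 = 1.33, a range that includes 1.

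The mismatch is plain for saturation and mild for rate.

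**4. Whether it changes the answer.** Take saturation with mean 97, SD 2, four time points, correlation 0.5 and a true difference of 1 point.

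- Variance of a patient's mean: 2² × (1 + 3 × 0.5)/4 = 2.5.
- At 60 per sequence: SE = √(2 × 2.5/60) = 0.289; 1/0.289 = 3.46; power ≈ Φ(3.46 − 1.96) = 93%.
- At 26 per sequence: SE = √(2 × 2.5/26) = 0.439; 1/0.439 = 2.28; power ≈ Φ(2.28 − 1.96) = 63%.

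GEE simulation (400 runs, values rounded and capped at 100):

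| Analysis | 60 per sequence | 26 per sequence |
|---|---|---|
| Poisson, dispersion estimated | 93.0% | 64.3% |
| Poisson, robust errors | 93.3% | 65.5% |
| Identity link, robust errors | 93.3% | 65.5% |

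The ratio of dispersion-estimated to robust SE was 1.00–1.01. For rate (mean 16, SD 3, difference 1.5 per minute, 26 per sequence) the same three analyses gave 64.5%, 65.0% and 65.3%. The scale hardly matters either: a drop from 97 to 96 is ln(97/96) = 0.0104 on the log scale, against 1/97 = 0.0103.

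**5. The one harmful route.** Poisson with dispersion held at 1 and model-based errors would do damage. The estimated dispersion averaged 0.039, so the SE would be inflated by about 1/√0.039 = 5.1. Power at 60 per sequence would then be roughly Φ(3.46/5.1 − 1.96) = 10%. The plan does not prescribe this.

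**6. Small-sample correction.** In 20,000 runs on patient means for saturation, false positives without and with a correction were 5.9% and 4.9% at 26 per sequence, and 5.7% and 5.3% at 60. Power for 1 point was 63.7% and 60.4% at 26, and 93.2% and 92.7% at 60. The gain is small and is paid for in power at the smaller size.

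**The case for a change.** The strongest case for a change is that the analysis plan names these two variables only in a test that cannot use the declared data, and that its recovery-room heading omits them. Taken literally, the nearest families suit saturation badly: at mean 97 a Poisson puts about 36% of its probability above 100%. Leaving the family open until the data are seen is what pre-specification is meant to prevent, and the remedy is a few words that need no new data.

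Part of this stands. The heading omits the two variables and no suitable family is named. Intraoperative rate and saturation are called secondary outcomes although the Objectives list them only for the PACU. Speaking of treatment conditions in the PACU is loose: patients there have had both depths, and the sequences differ in order and in planned depth at skin closure. An intraoperative rate comparison also needs the ventilator caveat when it is interpreted.

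The larger claim does not stand. The paired test does not purport to use PACU values; it is limited to readings within treatment periods. The Poisson clause is written for ordinal variables and does not bind an analyst faced with a continuous one. Substitution of one p-value for the other is conjecture, since the two sets of readings differ in place, schedule and test. The freedom left open is among choices that gave nearly the same answer.

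**Conclusion.** This is missing detail that a competent analyst fills sensibly, together with a labelling mismatch. Following the plan as written, one would fit the between-group GEE to PACU rate and saturation with a suitable family, and report the intraoperative comparison as intraoperative. Under the assumptions shown, ordinary choices differ by about one percentage point of power or less: 93.0–93.3% for saturation at 60 per sequence, 64.3–65.5% at 26. Their standard errors agree to within 1%. More explicit wording would gain clarity and an effect in natural units, with no material change in power, error rate or conclusion.

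This rests on assumed PACU means, SDs and correlation, and on the analyst not forcing the Poisson dispersion to 1 with model-based errors. Only two secondary outcomes are involved; the primary analysis and the calculation of 52 patients are unaffected. No change to the plan is called for.
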